PROTOCOL OF CLINICAL RESEARCH

Randomized Study to Assess the Impact of Mediterranean Diet Optimization on Metabolic Profile, Immune Activation, and Cardiovascular Risk in People with HIV on ART

Version of the protocol and date	Version: 1.2 date: 06/15/2024
Code of the protocol	
Qualification abbreviated either acronym	VIHMET
Promoter	
CRO (when proceed)	If applicable
Research Team	
Principal Investigator [name] HIV Division. Internal Medicine. Hospital del Mar [contact] e-mail: [contact]
 
Researcher(s) contributor(s) [name] Endocrinology Hospital del Mar, Barcelona [contact] e-mail: [contact]
 
[name] HIV Division. Internal Medicine. [contact] E-mail: [contact]
 
[name] Endocrinology Hospital del Mar [contact]

	
E-mail: [name]
 
[name] HIV Division. Internal Medicine. Hospital del Mar [contact] E-mail: [contact]
 
[name] HIV Division. Internal Medicine. Hospital del Mar. [contact] E-mail: [contact]

SUMMARY

Qualification	Randomized Study to Assess the Impact of Mediterranean Diet Optimization on Metabolic Profile, Immune Activation, and Cardiovascular Risk in People with HIV on ART
Goals	
 - Assess changes in metabolic profile and lipid in the week 24 - immunoactivation profile at week 24 - To assess changes in arterial stiffness levels measured by pulse wave velocity at week 24 - Proportion of participants with >20% decrease in TMAO in week 24 compared to baseline. - Proportion of participants with an increase of >2 points in the MEDAS scale of adherence to the Mediterranean diet at week 24 - Proportion of participants improving on the EQ-5D quality of life questionnaire at week 24 - Assess persistence of all changes from Objective 1 to 6 at Week 48 - To evaluate the presence and composition of coronary atherosclerotic plaque by means of coronary CT angiography before and after the intervention.
Design	Rehearsal clinical randomized open
Inclusion-exclusion criteria	
Criteria of inclusion:
 
 - Participant \geq 18 years. - Infection by HIV confirmed by serology. - Treatment antiretroviral asset (TAR). - Burden viral undetectable during to the less 12 months (HE allows a blip below 200 copies). - LDL >140 mg/ dL . - Mediterranean Diet Adherence Screener (MEDAS) less than 9 points (adherence low) for ease the detection of changes after the intervention. 
Criteria of exclusion:
 
 - Participants in treatment lipid-lowering. - Treatment with anti-inflammatory chronic. - Hepatitis B, C or Others conditions inflammatory chronicles active. - Hypercholesterolemia familiar No treated. - Hypothyroidism No controlled. - Impossibility of give he consent.
Treatments or interventions	Advice dietary, analysis blood, measurement of the pulse arterial
Variables	
Cholesterol total, cLDL, cHDL, triglycerides
 
Number, size and composition of particles of lipoproteins
 
Anthropometric profile
 
CD 3, CD45, CD4, CD8, CCR7, CXCR3, CCR6, CD103, FOXP3, CD25, CD45RA and CD45RO
 
IL-6, TNF-alpha, IFN-gamma, sCD163, sCD14, MADCAM-1, sCD14 and LPS.
 
Rigidity arterial extent by the speed of pulse
 
Trimethylamine -N-Oxide
 
Scale MEDAS of adherence to the diet Mediterranean

	Atheroma plaque (number of plaques) Plaque composition (% fibrosis, % calcium, % fat) Coronary calcium index
--	--

	Questionnaire of quality of life EQ- 5D
Population and No. subjects	100 patients of the unit of HIV
Participating centers	Hospital of the Sea. Barcelona
Study Description	Study comparative of the intervention dietetics conventional with a personalized dietary intervention
Overall duration from the study	January 2025- December 2026
Duration of the study for the patient	48 weeks

Board 1. Calendar of the study / procedures for a subject

	Screening (max 28 days before baseline visit)	visit (randomization)	W4 (+/- 7d)	W12 (+/-7d)	W24 (+/-7d)	W48 (+14-7d)
Type of visit	In person	In person			In person	In person
Intervention group			Virtual	Virtual		
Cluster control			No visit	No visit		
Informed consent	x					
Criteria of inclusion and exclusion	x					
Demographic data	x					
History medical	x					
Related story with HIV	x					
Exam physical		x			x	x
Anthropometric data		x			x	x
Questionnaires (MEDAS, FFQ, SMAQ, EQ- 5D and IPAQ)	x (only MEDAS)	x			x	x
Concomitant medication	x	x		x	x	x
Adverse effects		x		x	x	x
Test of pregnancy		x			x	x

if applicable						
Analytical studies	Valid available last 28 days	x			x	x
Sample storage		x			x	x
Pulse wave velocity		x			x	
Interview with nutritionist		x	x*	x*	x	
Noninvasive coronary artery angiography using CT (CCTA)		x				x

*Only cluster intervention

INDEX

1. List of abbreviations
2. History of versions
3. Frame theorist
 - 3.1. Background and justification of the study
 - 3.2. Hypothesis
4. Goals
5. Methodology
 - 5.1. Design of study
 - 5.2. Study population, inclusion/exclusion criteria and subject withdrawal criteria
 - 5.3. Definition of the variables of study
6. Procedures of the study
7. Period of the study
8. Methods statisticians
9. Aspects ethical
10. Management of samples
11. Confidentiality of the data
12. Literature
13. Annexes

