5. METHODOLOGY

5.1. Design of study

Study randomized prospective of intervention with optimization dietetics in people with HIV in treatment antiretroviral with dyslipidemia (Cholesterol total >200mg/dl either LDL cholesterol >160mg/dl) and without treatment lipid-lowering.

5.2. Study population, inclusion/exclusion criteria and subject withdrawal criteria.

Criteria of inclusion:

- Participant \geq 18 years.
- Infection by HIV confirmed by serology.
- Treatment antiretroviral asset (TAR).

- Burden viral undetectable during to the less 12 months (HE allows a blip below 200 copies).
- LDL >140 mg/ dL .
- Mediterranean Diet Adherence Screener (MEDAS) lower to 9 points (low adhesion) to facilitate the detection of changes after the intervention.

Criteria of exclusion:

- Participants in treatment lipid-lowering.
- Treatment with anti-inflammatory chronic.
- Hepatitis B, C or Others conditions inflammatory chronicles active.
- Hypercholesterolemia familiar No treated.
- Hypothyroidism No controlled.
- Impossibility of give he consent.

Criteria of withdrawal:

Subjects may withdraw from the study at any time without obligation to provide a reason. He IP can give of low to a subject of the study by reasons of safety or efficacy.

The reasons of abandonment of the study will be the following:

- Failed of screening: All patient that, a time informed is spoiled in participating in the study, does not meet the inclusion and/or exclusion criteria.
- Withdrawal of the consent: All patient that, by any reason, remove your consent
- Consumption of anti-inflammatory either lipid-lowering drugs during further of 7 days.
- Diagnosis of hypothyroidism either diabetes mellitus.
- Any event adverse that prevent continue any diet indicated.
- Loss of follow-up.

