***Cluster Intervention (67 participants):**

The intervention group will receive at the beginning a motivational interview with a personalized portfolio provided by a nutritionist on the Mediterranean diet and adherence to the diet: with information on the food components; desirable frequency of intake; recipes, use of olive oil, walnuts, hazelnuts and almonds. Individual guidelines will be planned individually to improve the lipid profile and improve food choices considering dietary habits, socioeconomic status and nutritional needs (and the score obtained on the MEDAS scale).

At weeks 4 and 12 (virtual), the patient will have a new interview with the nutritionist to review the recommendations, discuss difficulties with diet adherence, design weekly dietary plans and shopping lists. At week 24 and 48, an in-person visit will be held to perform all the procedures of the baseline visit again (including blood draws).

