***Cluster treatment standard (33 participants).**

Baseline visit (in person), In addition to the initial assessment identical to that of the intervention group, general dietary information will be provided in writing, as is currently done in the HIV unit.

New visits will be made at week 24 (in person) and week 48 (in person). The same measurements, dietary assessments and blood draws will be made as at the baseline visit.

Detailing of tasks to carry out for achievement of the goals:

- Task 1. Adherence to the Mediterranean diet, anthropometric and quality of life measurements (objectives 5 and objective 6). All carried out by a trained researcher.
 - Task 1a. 118-item semiquantitative food frequency questionnaire (FFQ), MEDAS questionnaire, and a 24-hour dietary recall .
 - Task 1b. Anthropometric measurements: height and weight will be measured using a mechanical anthropometric scale. BMI (BMI = weight (kg) / [height (cm)]2). Waist circumference halfway between the lower rib margin

and the iliac crest. Hip circumference will be measured as the widest measurement over the buttocks.

- Task 1c. Measuring quality of life using the EQ-5D questionnaire. Specific questions on alcohol consumption patterns and the IPAQ Physical Activity Questionnaire, Simplified Medication Adherence Questionnaire (SMAQ).
- Task 2. Measurement of the profile lipid (for achievement of goals 1 (1a,1b,1c)
 - Task 2a. Blood collection after fasting for more than 8 hours, between 8am and 10am. Serum will be obtained for the usual clinical measurement by means of the practice clinic usual and in the laboratory of Reference from Catalonia for the measurement of total cholesterol, HDL and LDL (according to standard practice). Serum, plasma and cells will be preserved (task 4)

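### The visit calendar marks adverse effects and concomitant medication at week 12 for everyone, but controls have no week-12 contact, so scheduled checks up to week 24 are 2 in the intervention arm and 1 in control

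*Protocol*

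**What the plan says.** Board 1 of the Protocol has columns for screening, baseline and weeks 4, 12, 24 and 48. The row "Adverse effects" is marked at baseline and weeks 12, 24 and 48. The row "Concomitant medication" is marked at the same visits and also at screening. Neither row carries a star. The footnote "Only cluster intervention" is attached only to the week-4 and week-12 entries of the nutritionist interview.

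The visit-type rows at the top of the same table give the intervention group a virtual contact at weeks 4 and 12. The row "Cluster control" shows no visit at either time.

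Section 6 agrees with the visit-type rows. For the intervention arm: "At weeks 4 and 12 (virtual), the patient will have a new interview with the nutritionist". For the standard arm: "New visits will be made at week 24 (in person) and week 48 (in person"). No telephone or other remote contact with controls is described.

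Section 5.2 lists among the reasons for leaving the study "Consumption of anti-inflammatory either lipid-lowering drugs during further of 7 days" and "Any event adverse that prevent continue any diet indicated".

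**The concern.** The two week-12 marks nominally apply to all participants, yet one arm has no contact at which the information could be collected. Either the table contradicts itself, or ascertainment is unequal by design. On both readings, only the intervention arm can be asked at week 12.

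Two things are at stake. First, any table of adverse effects or drug use by arm would partly reflect how often people were asked. Second, both items bear on reasons for leaving the study. Participants enter with raised LDL and without lipid-lowering treatment, and the main variables in section 5.3 are lipids, so lipid-lowering drugs act directly on the outcome. An intervention participant who starts such a drug early can be identified at week 12 and leave before the week-24 sample. A control who does the same has no scheduled check until week 24 itself. The trial is open, so blinding does not even out reporting or decisions on withdrawal.

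**Working it through.** The Protocol states no figure on this point, so there is none to reproduce. The check is a count from the calendar, followed by an illustration under stated assumptions.

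**Scheduled checks per participant after baseline** (the same for adverse effects and for medication)

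| | Intervention | Control |
|---|---|---|
| Week 12 | 1 (virtual contact) | 0 (no visit) |
| Week 24 | 1 | 1 |
| Week 48 | 1 | 1 |
| Up to week 24 | 2 | 1 |
| Overall | 3 | 2 |
| Longest gap before week 24 | 12 weeks | 24 weeks |

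The control column rests on both the visit-type row of Board 1 and the visit schedule in section 6, so it does not depend on how the table was read from the PDF.

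**Illustration of the effect on detection by week 24.** Assumptions, none of them from the documents:
- each contact detects an event that has already happened with probability p, between 0.5 and 0.8;
- contacts are independent;
- the true event rate is the same in both arms;
- a fraction f of the events up to week 24 occurs before week 12.

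An event before week 12 meets two contacts in the intervention arm, and an event after week 12 meets one. In control every event meets one.

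- Control: D_C = p
- Intervention: D_I = f[1 − (1 − p)²] + (1 − f)p
- Ratio: D_I / D_C = f(2 − p) + (1 − f) = 1 + f(1 − p)

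With events spread evenly over 24 weeks, f = 0.5:

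- p = 0.5: D_I = 0.5 × 0.75 + 0.5 × 0.5 = 0.625, against 0.50; ratio 1.25
- p = 0.8: D_I = 0.5 × 0.96 + 0.5 × 0.8 = 0.88, against 0.80; ratio 1.10

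For events before week 12 alone (f = 1) the ratios are 1.5 and 1.2. For events after week 12 (f = 0) the ratio is 1.

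Poorer recall in controls over the longer gap would widen the ratio. Positive dependence between contacts, where an event missed once tends to be missed again, would narrow it.

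**The case against.** The strongest reply is that the inconsistency has little consequence. Objectives 1 to 8 and the variables in section 5.3 include no adverse-event outcome, so no comparison of adverse events between arms is planned. The intervention is dietary advice. Both arms have medication and adverse effects recorded at weeks 24 and 48, and nothing restricts those entries to current use, so earlier events and drug use in controls can be recovered by recall. Section 5.2 does not say which record or visit triggers withdrawal, nor that withdrawn participants are left out of the analysis. Analysis sets and the handling of drug use during follow-up may be settled in an SAP that is not shown.

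Much of this stands, and it limits the point. The difference is in the frequency and timing of ascertainment; controls are not left unasked altogether.

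A reader might infer that the week-24 lipid and inflammation comparison is biased. The documents show only that it could be: they give neither a direction nor a size, and do not show that anyone would be withdrawn because of a week-12 record. A reader might also apply the ratio of 1.2 to 1.5 to the whole period up to week 24. That would give every event two contacts, although events after week 12 cannot be reported at week 12.

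The reply does not remove the contradiction in Board 1. Nor can an analysis plan recover reports that were never solicited, or week-24 samples not taken because someone had already left.

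**Conclusion.** The calendar contradicts itself. As written, it gives 2 v 1 scheduled checks up to week 24 and 3 v 2 overall. This would make any tabulation of adverse effects or concomitant medication by arm non-comparable, and it could make retention into the week-24 comparison differ by arm through the withdrawal reasons in section 5.2. Bias in the lipid or inflammation results is possible but not demonstrated.

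The size cannot be estimated from the documents. The detection ratio of about 1.10 to 1.25 at week 24 is illustrative and rests on the assumed 50-80% detection per contact, independent contacts and evenly spread events. The point is modest but worth correcting, because the correction costs almost nothing.

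**What to change.** - **Reconcile Board 1.** Make the week-12 marks for adverse effects and concomitant medication agree with the visit-type rows. One way is to star them as intervention-only monitoring. The documents do not show whether that was the intention or whether a control contact was meant, so the investigators must say which.
- **Use the same record in both arms.** At weeks 24 and 48, collect both items on one form with the same questions, covering the whole interval since the last in-person visit (baseline to week 24, then week 24 to week 48). Use that record for any comparison between arms. The checks that enter a comparison are then 2 v 2.
- **Reconcile section 5.2 with the calendar.** State how the drug-use and adverse-event reasons for leaving the study are ascertained, so that it is done in the same way in both arms. This should not limit safety monitoring or the investigator's ability to withdraw a participant for safety.

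Cost: a footnote, a look-back question on a form already scheduled, and a clarifying sentence, with no added visits. The downside is a longer recall period, but it is equal in both arms.

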1. LIST OF ABBREVIATIONS

HIV	Virus of the immunodeficiency human
PLHIV	Person that lives with he HIV
TAR	Treatment antiretroviral
AIDS	Syndrome of immunodeficiency acquired human
LDL	Lipoproteins of low density
MRI	Resonance magnetic nuclear
TMAO	N-oxide of trimethylamine

2. HISTORY OF VERSIONS

Version	Date	Description of the change	Brief justification
1.2	June 15, 2024	Introduction to the amendment Noninvasive coronary artery angiography using CT (CCTA)	Given the possibility of having CCTA experience for coronary plaque detection at our center, this amendment is included to evaluate subclinical coronary disease and possible changes.

3. FRAME THEORIST

3.1 BACKGROUND AND JUSTIFICATION OF THE STUDY

Since the implementation of highly active antiretroviral therapy (ART), HIV-related mortality has been dramatically reduced. Morbidity and mortality are no longer caused by acquired immunodeficiency syndrome. Liver disease, cardiovascular disease, and non-AIDS-defining malignancies are the main causes of death. Compared with the general population, people living with HIV (PLHIV) have some degree of chronic immune activation leading to accelerated immune senescence. This process may drive the development of more non-AIDS-related comorbidities compared with uninfected individuals. By it so much, the PLHIV develop further events cardiovascular (MACE). Finding new targets to reduce cardiovascular risk is critical to decreasing MACE and improving the quality of life of PLHIV. Multiple mechanisms may drive these non-AIDS-related events, such as chronic immune activation, inflammation, and treatment side effects. ART use has been associated with metabolic complications such as dyslipidemia, endurance to the insulin and distribution altered of the fat. Besides, These metabolic complications have been linked to an increased risk of myocardial infarction and cardiovascular disease. Different types of ART appear to have a different impact on the metabolic/lipid profile.

Diet also has a role in metabolic control independently of ART. The impact of dietary intake of saturated fat and cholesterol on lipids The relationship between serum cholesterol and subsequent development of cardiovascular disease has been consistently demonstrated. On the contrary, the degree of dietary fat and cholesterol intake, the composition of that fat and the interaction of ART in PLHIV have an impact a stranger in the levels of lipids serum. Several studies previous to

Small-scale studies in HIV-infected individuals demonstrated no relationship between saturated fat intake and serum lipid levels.

Profile lipid

HIV infection is known to be associated with a highly atherogenic pattern characterized by increased levels and reduced size of low-density lipoproteins (LDL) and decreased levels of high-density lipoproteins. The key factor in the relationship between he HIV and the dyslipidemia go on without stay up late. The infection by HIV and ART are probably involved. In any case, the consequence of this persistent dyslipidemia could increase cardiovascular risk and the progression of atherosclerosis, which in addition to persistent inflammation could increase MACE. The standardization of the determination of LDL cholesterol (cLDL) is technically complex. This fact, together with the variability of some lipid components between individuals, has generated difficulties in the interpretation of the results of the lipid profile and its association with cardiovascular risk. The conventional methods of lipoprotein quantification used in clinical laboratories only allow the quantification of concentrations. Therefore, it is necessary to find new techniques capable of estimating cardiovascular risk with greater precision. This requires the ability to distinguish between different classes and subclasses of lipoproteins and to quantify particle size using nuclear magnetic resonance (NMR) spectroscopy. NMR has been shown to be a more accurate technique in different types of population. To date, few studies have been conducted using NMR in people living with HIV. With NMR we can estimate with precision he risk cardiovascular to the identify and quantify different types of lipoproteins according to their physicochemical characteristics, which allows determining with greater precision and accuracy the degree of penetration of these particles into the endothelium vascular. This technique can allow us have a better comprehension of quantitative and qualitative changes in lipoprotein profiles. Some studies explored the relationship between lipoprotein subclass profiles assessed by MRI and subclinical atherosclerosis by noninvasive means, such as intima-media thickness or aortic pulse wave velocity.

Speed of vibe of pulse

Arterial stiffness may lead to the development of vascular complications and premature vascular aging . It is a reliable biomarker of cardiovascular damage. Aortic pulse wave velocity is an indicator of aortic stiffness and is used as a predictor of adverse cardiovascular events. In addition, this technique is able to detect changes before intima-media thickness. Data on arterial pulse wave velocity in PLHIV are scarce. Since it is a simple, noninvasive technique, it could be useful to assess cardiovascular risk in this population.

Biomarkers metabolic of risk cardiovascular

Trimethylamine N-oxide (TMAO) is a gut microbiota-dependent metabolite generated from the oxidation of trimethylamine . TMAO is an independent cardiovascular factor related to inflammation, oxidative stress, cardiac fibrosis, endothelial injury, hypertension, and platelet activation. PLWH are potentially more susceptible to TMAO due to increased intestinal permeability. Increased intestinal permeability would increase the translocation of this bacterial product and, consequently, increase immune activation and inflammatory cytokine expression. The Diet has an impact on TMAO. Vegetarians have reduced TMAO levels

while people who did not follow the Mediterranean diet had increased levels according to two studies. Dietary changes in TMAO measurements have not been investigated before in HIV infection. Acting on the intestinal microbiota and the diet could be a via potential for reduce the risk cardiovascular in PLWH. Any impact on diet and lifestyle could change the TMAO profile and could be considered as an indirect marker of cardiovascular disease, in a via different to the metabolism lipid. His measurement could provide additional information on lipids and be an outcome of interest to evaluate the result of a dietary intervention.

Risk cardiovascular and activation immunological

Previous studies in HIV have separately associated subclinical atherosclerosis with markers serum of inflammation, activation widespread of cells T, activation of cytomegalovirus-specific T cells and soluble CD163 (a marker of monocyte activation). The role of T cells and the adaptive immune response in atherosclerosis has long been known. Although murine models suggested that CD4+ cells may be more atherogenic than CD8+ cells within plaques, circulating CD8+ cells can also promote atherosclerosis in response to activation by intracellular infections such as cytomegalovirus or *Chlamydia pneumoniae*. Kaplan et al have shown that in HIV, CD8+ activation may be more predictive of carotid plaque whereas CD4+ activation is more closely associated with carotid stiffness, another measure of disease vascular subclinical. All the data clinical published until the moment suggest that exists a narrow relationship between the activation immunological derivative of HIV infection and the extent of cardiovascular damage.

Diet Mediterranean in PLHIV

The Mediterranean diet, supplemented with virgin olive oil and nuts, has shown, in people at high cardiovascular risk, a reduction in MACE in primary and secondary prevention. The Mediterranean diet has also been associated with a reduction in age-related inflammation. Stradling et al. conducted a feasibility study in PLWH who adopted a Mediterranean portfolio diet supplemented with walnuts reducers of fat. The results They suggested improvements in blood pressure, LDL cholesterol, and diet quality after 6 months. Another study in PLWH showed improvement in metabolic parameters, immune activation, regulatory T cell subsets, and microbiota.

Noninvasive coronary artery angiography using CT (CCTA)

Noninvasive coronary angiography using computed tomography allows a detailed and noninvasive assessment of the coronary arteries, their anatomy, the presence of atherosclerotic plaques, their location and level of severity, and the presence of qualitative characteristics in the plaques that increase their risk of rupture. Currently, CCTA can be performed with very low doses of radiation (around 3 mSv), and the total time of the test is just a few minutes. The test requires the use of intravenous contrast for a better definition of the coronary lumen, although relevant complications associated with the use of contrast are very rare. Due to its advantages, CCTA has become a key test in the assessment of patients with stable chest pain, it is recommended as a class I test by the guidelines of the European Society of Cardiology (), and its clinical use is increasing rapidly in our environment.

In conclusion, the Mediterranean diet in the general population with cardiovascular risk factors reduced the incidence of major adverse cardiovascular events. In PLWH, the diet Mediterranean has shown some improvements immune and metabolic. Reduce the risk

cardiovascular associated to the HIV is at the moment one of the Main objectives of the investigation in HIV. HE they have identified several techniques for estimate the risk, but we do not yet have an adequate tool to reduce it.

3.HYPOTHESIS

This study HE base in the following hypothesis:

1. HIV infection and ART negatively impact the lipid profile of people living with HIV.
2. HIV infection is associated with an increase in cardiovascular disease through different pathways (classical risk factors, persistent inflammation, antiretroviral treatment, etc.).

3. The infection HIV HE associates to a profile lipid abnormal so much of the cholesterol total, HDL, LDL and lipoprotein subclasses measured by proton magnetic resonance imaging.
4. HIV infection drives early atherosclerosis mediated, in part, by an adverse lipid profile and persistent immune activation.
5. Modifying the diet towards a Mediterranean diet will produce changes in the lipid profile, in immunoactivation markers, in inflammatory parameters, in clinical markers of subclinical atherosclerotic disease such as the pulse wave and in markers of metabolites associated with cardiovascular disease such as serum Trimethylamine -N-Oxide (TMAO).

4. Objectives

Based in the previous hypothesis We propose the following Objectives:

Objective 1. Evaluate changes in the metabolic and lipid profile:

- Objective 1a. To evaluate changes in the lipid profile (total cholesterol, LDL-C, HDL-C, triglycerides) at week 24 compared to baseline.
- Objective 1b To evaluate the number, size and composition of lipoprotein particles by proton magnetic resonance spectroscopy at week 24 compared to baseline.
- Objective 1c. Percentage of people with increased high-density lipoprotein (HDL) levels >5%.
- Objective 1d. To assess changes in the anthropometric profile (weight, body mass index, abdominal circumference) at week 24 compared to baseline.

Aim 2. Assess changes in he profile inflammatory and of immunoactivation :

- Aim 2a. Assess the changes in the activation immune of the T cell compartment at week 24 compared to baseline.
- Objective 2b. Percentage of patients with reduced inflammatory and bacterial translocation markers at week 24 compared to baseline.

Objective 3. To evaluate changes in arterial stiffness levels measured by pulse wave velocity at week 24 compared to baseline.

Aim 4. Proportion of Participants with decline of >20% of TMAO in the week 24 compared to baseline.

Aim 5. Proportion of Participants with increase of >2 points in the scale MEDAS adherence to the Mediterranean diet at week 24 compared to baseline

Objective 6. Proportion of participants who improve in the quality of life questionnaire. EQ-5D life at week 24.

Objective 7. Evaluate the persistence of all changes included in objectives 1 to 6 at week 48 (24 weeks after the end of the intervention)

Objective 8. To assess the burden of subclinical atherosclerotic coronary disease and changes 1 year after intervention.

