5.3. Definition of the variables of study

Main Variables

- Total cholesterol, cLDL , cHDL , triglycerides in mg/ dL . It will be measured at baseline, week 24 and 48.

Secondary Variables

- Number, size and composition of lipoprotein particles by proton magnetic resonance spectroscopy at baseline, week 24 and 48.
- Anthropometric profile (weight, body mass index, abdominal circumference) at baseline, week 24 and 48.
- CD 3,CD 45,CD4,CD8,CCR7,CXCR3,CCR6,CD103,FOXP3,CD25,CD45RA and CD45RO. Quantification in blood in visits basal, 24 weeks and 48 weeks of cells with markers.
- IL-6, TNF-alpha, IFN-gamma, sCD163, sCD14, MADCAM-1, sCD14 and LPS. Quantification in serum in visit basal, 24 weeks and 48 weeks of
- Rigidity arterial extent by the speed of vole of pulse in the visit basal, week 24 and 48.
- Levels of Trimethylamine -N-Oxide serum (TMAO) in the in the visit basal, week 24 and 48.

- Scale MEDAS of adherence to the diet Mediterranean measures in the Baseline visit, week 24 and 48
- Questionnaire of quality of life EQ-5D in the visit basal, week 24 and 48.
- Presence of atheromatous plaque at the coronary level at the baseline visit and at week 48
- Presence of calcium, fibrous and fatty fraction in the coronary plaque at the baseline visit and at week 48
-

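### Objective 6 measures quality of life only as the proportion who improve on EQ-5D, which discards information that the trial already collects; a baseline-adjusted score comparison would be a cheap improvement to this secondary outcome

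*Protocol*

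**What the plan says.** Section 4, Objective 6, reads "Proportion of participants who improve in the quality of life questionnaire", naming EQ-5D and week 24. The Summary (Goals) has the same measure: "Proportion of participants improving on the EQ-5D quality of life questionnaire at week 24". Objective 7 carries it to week 48. Neither place sets a threshold for improvement or names the EQ-5D score to be used; the annex list shows that the instrument is the EQ-5D-5L.

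Section 5.3 lists as a secondary variable "Questionnaire of quality of life EQ-5D in the visit basal, week 24 and 48", without a summary measure. The calendar of procedures applies the questionnaire in both arms at baseline, week 24 and week 48.

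MEDAS is treated differently. Its objective has a threshold ("Proportion of Participants with increase of >2 points in the scale MEDAS adherence to the Mediterranean diet at week 24 compared to baseline"), and section 5.2 limits entry to scores below 9, giving as the reason "low adhesion) to facilitate the detection of changes after the intervention". No entry criterion requires room to improve on EQ-5D.

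**The concern.** Scoring each participant as improved or not loses information in three ways.

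- **Best score at baseline.** EQ-5D has a best possible state. Whoever reports it at baseline is a fixed non-success in either arm, whatever the diet does.
- **Worsening.** Unchanged and worse fall in the same category. If the diet prevents worsening, or causes it, the proportion improved may not show it.
- **Size of change.** A small and a large gain count the same.

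A neutral Objective 6 could then reflect the scoring rule and not the diet, and a favourable one could coexist with more participants getting worse. With 33 controls there is little information to spare.

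**Working it through.** The protocol gives no power, alpha, expected rate or EQ-5D distribution for this objective, so there is no stated figure to reproduce. The arm sizes, 67 and 33, are from section 6. Everything else is assumed: two-sided 5% test, no dropout, share *c* at the best score of 0, 20, 35 or 50%, equal in both arms.

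**1. Effect of the ceiling on a responder proportion.** Let *p* be the proportion improving among those able to improve. The observable rate is (1 − c)p in each arm, so the absolute difference is multiplied by (1 − c) and the risk ratio is unchanged. Take 75% v 50% among those able to improve. Power = Φ[(difference − 1.96 × SE0)/SE1], where SE0 uses the pooled and SE1 the separate proportions.

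For c = 35% the rates are 0.4875 v 0.325 and the pooled rate is (67 × 0.4875 + 33 × 0.325)/100 = 0.434. Then SE0 = 0.1054, SE1 = 0.1019, and Φ[(0.1625 − 1.96 × 0.1054)/0.1019] = Φ(−0.43) = 33%.

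| Share at best score | Rates, diet v control | Difference | Risk ratio | Power |
|---|---|---|---|---|
| 0% | 75 v 50% | 25 points | 1.5 | 70% |
| 20% | 60 v 40% | 20 points | 1.5 | 47% |
| 35% | 49 v 33% | 16 points | 1.5 | 33% |
| 50% | 38 v 25% | 12.5 points | 1.5 | 23% |

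**2. Proportion improved against the baseline-adjusted mean.** Simulation: normal score, baseline to week-24 correlation 0.6, benefit 0.5 SD in the diet arm, both visits capped at the (1 − c) baseline quantile and rounded to steps of 0.2 SD. Any step upward counts as improved. Both analyses use the same capped scores.

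| Share at best score | Power, proportion improved | Power, baseline-adjusted mean |
|---|---|---|
| 0% | 56% | 84% |
| 20% | 34% | 76% |
| 35% | 23% | 70% |
| 50% | about 15% | about 60% |

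Repeat runs agree within about 2 percentage points. At a 35% ceiling, about 16% (diet) v 35% (control) worsen, a difference that the stated measure does not use.

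**3. Where the gain comes from with no ceiling.** The factor √(1/67 + 1/33) is 0.2127. The SD of the change is √(2 × (1 − 0.6)) = 0.894, so the standardised benefit is 0.5/0.894 = 0.559.

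- Improved or not: Φ(0.559) = 71% v 50%, power about 55%.
- Mean change: Φ(0.559/0.2127 − 1.96) = Φ(0.67) = 75%.
- Baseline-adjusted mean: residual SD √(1 − 0.6²) = 0.8, standardised benefit 0.5/0.8 = 0.625, Φ(0.625/0.2127 − 1.96) = Φ(0.98) = 84%.

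About 20 of the 29 points come from not dichotomising and about 9 from the baseline adjustment.

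**4. Ignoring worsening can mislead either way.** Invented percentages, improved/unchanged/worse:

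| Example | Control | Diet | Difference in improvers | Difference in (improved − worse) |
|---|---|---|---|---|
| A | 25/45/30 | 25/65/10 | 0 | (25 − 10) − (25 − 30) = +20 |
| B | 25/65/10 | 40/25/35 | +15 | (40 − 35) − (25 − 10) = −10 |

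In A a real benefit is missed. In B a net harm looks like a benefit.

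**The case against.** The strongest reply has five parts.

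- **The outcome is secondary and the style is consistent.** The main variables are lipids, the hypotheses do not predict a quality-of-life effect, and Objectives 1c, 2b, 4 and 5 are also proportions. This stands and limits the weight of the point.
- **An analysis plan not shown could add a score analysis.** It could, and the choice of score is ordinary analysis-plan content. But the protocol does not leave the type of measure open: it states a proportion in two places, and an added analysis would leave Objective 6 as it is.
- **The ceiling is assumed.** This stands. A reader might infer from the entry criteria (treated, virally suppressed, no active hepatitis) that a large group starts at the best score. None of those criteria measures quality of life, and the background describes more comorbidity in this population. The documents do not support any particular share.
- **Part of the loss belongs to the instrument.** This stands. The preferred analysis also falls, from about 84% to about 60%. That loss is already in the comparison, and the gap remains.
- **The simulation suits the remedy.** A uniform shift does favour a comparison of means, and counting any step as improvement is an assumed rule because the protocol gives none. The figures are illustrations and refute no claim in the protocol.

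Two stronger readings are tempting. One is that the rule shrinks any real difference between the arms. It does not: with equal ceiling shares the risk ratio is unchanged, and example B shows that the rule can also favour the diet falsely. The other is that chance imbalance in participants at the best score is a further defect. That variation is already part of the binomial variance of the proportion, so a standard test allows for it.

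**Conclusion.** The point holds as one of wasted information and incomplete measurement in a secondary outcome. It is not an error that threatens the trial. That a participant at the best baseline score cannot succeed, and that worsening is pooled with no change, follows from the wording of Objective 6 without any assumption.

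The size does rest on assumptions. Under a 0.5 SD benefit, correlation 0.6 and 67 v 33 analysed, the baseline-adjusted mean has about 28 percentage points more power with no ceiling (84 − 56) and about 45 more with half at the best score (60 − 15). The real ceiling share, and so the place within that range, cannot be known from the documents. The case for change does not depend on it, because the gain is already there at a share of zero.

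**What to change.** In Objective 6 and in the Summary, replace the proportion improving with the between-arm difference in one named EQ-5D-5L score (for example the index) at week 24, adjusted for the baseline score. Let Objective 7 repeat the same comparison at week 48. As description, report by arm the numbers improved, unchanged and worsened, and the number at the best score at baseline.

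The cost is the rewording of one secondary objective and one baseline-adjusted model. The questionnaire is already scheduled in both arms at all three time points, so no data, visits or participants are added. The small downside is that a mean difference is less immediate to read than a percentage; the descriptive table keeps the percentage available.
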